11.3. Criteria for significance

For behavioral, EEG/ERP and self-report measures alone, a statistical effect exceeding an α -level of 0.05 will be considered statistically significant. The appropriate adjustments for multiple comparison follow-up tests (e.g., Bonferroni, Tukey, Scheffe) will be employed where necessary. For the fMRI analysis, where ROIs are stipulated a priori, the threshold for statistical significance will also be set at an α -level of 0.05. For whole-brain analyses, probability thresholding of individual voxels is used in combination with minimum cluster size thresholding to increase statistical power whilst minimizing the chance of type 1 errors. The underlying principle is that true regions of activation will tend to occur over contiguous voxels whereas noise has much less of a tendency to form clusters of activated voxels. Although tables of false detection probability vs. cluster size have been published, they are limited to 2D images, and are not directly applicable; even if tables were published, they could not cover every possible combination of experimental parameters. Therefore, we empirically investigate the tradeoff between probability and cluster threshold to achieve the desired significance level for a particular experimental condition.

The AlphaSim program (within AFNI) is a Monte Carlo simulation technique that provides a method for multiple comparison correction while persevering statistical power. Using random image generation, Gaussian filtering (to simulate voxel correlations), thresholding, and tabulation of cluster size frequencies, the program generates an estimate of the overall significance level achieved for various combinations of probability and cluster size thresholds assuming spatially uncorrelated voxels. Overall, our simulations indicate that by accepting a minimum cluster size it is possible to obtain an order-of-magnitude improvement in probability threshold over the value of probability threshold required if cluster size thresholding is not used. An approximately 200-400 μ l minimum cluster size will generally be used in these studies to maintain our alpha level of 0.05. The criteria for significance (alpha) will be 0.05.

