All scanning experiments will be performed on a research-dedicated 3T MRI scanner, located at the NIDA-IRP. The 3T MRI machine used in this protocol is FDA approved and is used as a data collection tool. This study may use the MRI in research mode, including custom pulse sequences. All sequences, including those in research mode, are within FDA approved specific absorption radiation (SAR) limits. No additional risk is incurred in research mode, and we are not testing sequences to evaluate safety or risk.

Participants' heads will be placed inside the RF coil and held in place by a head restraint that may consist of soft foam, a vacuum bag, a bite bar and/or hardened polyurethane foam (expanding packing foam). For most scanning experiments, a blipped, gradient-echo, echo-planar image (EPI) pulse sequence (e.g. TE = 27ms) is used with a TR of about 2 seconds. Images will be acquired with an in-plane resolution of 64 x 64 and with a 22cm field of view. Specific imaging parameters (e.g. number of slices, slice angle, TR, TE, flip angle etc.) may be changed in order to maximize signal integrity. Please note, that we use a "watchdog" program that runs continuously on the MRI computer during the execution of all pulse sequences and ensures that no scanning parameter ever exceeds FDA guidelines. The MRI is used as a data collection tool. All sequences and scans conducted are within FDA approved parameters, and the scans are not conducted to assess safety or efficacy of the scans themselves.

6) AM Scan Session (note: all times approximate and order of scans generally fixed but may be switched in the event of instrument problems or subject compliance).

Principal Investigator: [name].

Structural Images. A set of high resolution structural MR images will be collected. The images will be acquired using a T1-weighed three-dimensional MPRAGE sequence and will be used for the display of functional data. Completion time: ~5 min.

Date: March 2, 2022

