11.4. Power analysis

General fMRI power. Since fMRI is the main outcome measurement utilized in the present protocol, the key power analysis pertains to the fMRI data. However, prospective power analyses for fMRI data are complicated for several reasons. First, fMRI data are analyzed in a hierarchal manner such that both the intraparticipant variance from the time-course data and the inter-participant variance across individuals could affect statistical power. A large number of time points tend to mitigate effects of intra-participant variance, but temporal autocorrelation and scanner limitations limit the number of independent measurements per unit time and thus the number of independent time points that are collected. In addition, effect sizes and both types of variance will vary spatially. Because of this, a given study may have sufficient power to detect differences in some brain regions, but lack sufficient power in other regions where the null hypothesis is false. Finally, fMRI analysis consists of a very large number of non-independent multiple comparisons, greater than 1.5 million at the group level, necessitating correction methods less severe than a Bonferroni correction, as discussed above. Thus, a proper power analysis on fMRI data requires simulating all of these effects. Desmond and Glover (2002) have performed such a simulation. They show for a relatively modest signal change of 0.5% during a cognitive task and with an intra-participant standard deviation of 0.75% and an inter-participant standard deviation of 0.5%, that 11 participants are required for a power of 0.8 using p < 0.05. Using a false positive rate of p < 0.002, a level more consistent with a cluster size threshold to correct for multiple comparisons (Forman et al., 1995), and with the variances kept the same, approximately 21 participants are needed for an expected signal change of 0.5% and

Principal Investigator: [name].

11 participants for a signal change of 0.75%. For more than \sim 100 independent time points, power (and hence the intra-participant variance) is relatively independent of the number of time points (Desmond and Glover, 2002). All current analyses should fall within this range.

Date: March 2, 2022

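### The 200-400 microlitre cluster rule cannot be shown to hold whole-brain alpha at 0.05, because Section 11.3 fixes neither voxel-wise p nor smoothness; at p < 0.002 it fails above about 5-6 mm FWHM

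*Combined protocol and SAP*

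**What the plan says.** Section 11.3 treats a priori regions and whole-brain maps separately. Regions are tested at 0.05. For whole-brain maps, "probability thresholding of individual voxels is used in combination with minimum cluster size thresholding". The trade-off between the two thresholds is to be explored by AlphaSim simulation for the experimental condition at hand. A typical extent of about 200-400 microlitres follows: this "minimum cluster size will generally be used in these studies to maintain our alpha level of 0.05". The section closes with "The criteria for significance (alpha) will be 0.05".

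No voxel-wise p, sidedness, connectivity or smoothness is given, and the pre-processing section (11.1) names no smoothing kernel. The sentence describing the simulation lists "Gaussian filtering (to simulate voxel correlations") among its steps and ends with "assuming spatially uncorrelated voxels".

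The one related voxel-level figure is in the power section, 11.4: "Using a false positive rate of p < 0.002, a level more consistent with a cluster size threshold to correct for multiple comparisons". Section 24.12 carries Section 11 over to the tDCS arm, so both imaging arms use the same rule.

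**The concern.** The largest cluster that noise alone produces grows quickly as the data become smoother, and shrinks as the voxel threshold becomes stricter. A volume range quoted without either input has no error rate attached to it. An analyst could follow Section 11.3 exactly, report clusters of 200 microlitres as corrected at 0.05, and have a true family-wise error anywhere from near zero to near one.

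The description of the simulation adds to the doubt. Gaussian filtering makes voxels correlated, so a simulation that includes it does not assume uncorrelated voxels. If the uncorrelated description were the operative one, it would be the assumption that most understates the extent needed.

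Whole-brain BOLD maps belong to primary outcome 1, and Section 11.4 calls fMRI the main outcome measurement, so the control of false positives there should be open to verification.

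**Working it through.** **Inputs from the documents**
- Cluster extent 200-400 microlitres and target alpha 0.05 (Section 11.3).
- Voxel p: not stated in Section 11.3; 0.002 appears in Section 11.4.
- Smoothness: not stated.
- In-plane voxel size, from "Images will be acquired with an in-plane resolution of 64 x 64 and with a 22cm field of view" (Section 4.4): 220 / 64 = 3.44 mm.
- Number of comparisons: "greater than 1.5 million at the group level" (Section 11.4).

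**Assumptions**
- 4 mm slices. Voxel volume is then 3.44 x 3.44 x 4 = about 47 microlitres, so 200 and 400 microlitres are 200/47 = 4.2 and 400/47 = 8.5 native voxels.
- An ellipsoid search volume of 1.4-1.5 L (1.5 million comparisons at 1 cubic mm each is 1.5 L).
- Stationary Gaussian noise and face-connected clusters.

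**Method**
1. Generate Gaussian noise in the mask, smooth it to a given FWHM and standardise it.
2. Threshold at z = 3.09 (two-sided p 0.002) or z = 2.88 (one-sided p 0.002), and likewise for other p values.
3. Record the largest cluster in each null map.
4. Family-wise error = share of maps whose largest cluster is at or above the cut-off. Extent needed = 95th percentile of the largest cluster.

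The grids were native (400-500 maps), 2 mm (240 maps) and 1 mm (80 maps). The Monte Carlo margin at an error of 0.05 is 1.96 x sqrt(0.05 x 0.95 / n): about 0.02 for n = 500 and 0.05 for n = 80.

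**The plan's own range.** It cannot be reproduced from the documents, because two inputs are missing. Two assumed settings return roughly that range: voxel p 0.002 with 5-6 mm FWHM (189-448 microlitres needed), and voxel p 0.05 with uncorrelated native voxels (236-378 microlitres needed). The documents do not say which, if either, was used.

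**Results at voxel p 0.002** (ranges cover sidedness, grid and mask)

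| FWHM | Error at 200 microlitres | Error at 400 microlitres | Extent needed for 0.05 (microlitres) |
|---|---|---|---|
| 4 mm | 0 | 0 | 95-142 |
| 5 mm | 0.02-0.19 | at most 0.01 | 189-256 |
| 6 mm | 0.30-0.78 | 0.01-0.08 | 330-448 |
| 7 mm | 0.77-0.95 | 0.12-0.25 | 470-576 |
| 8 mm | 0.92-0.99 | 0.25-0.58 | 607-804 |
| 10 mm | 0.99 or more | 0.75-0.86 | 1,096-1,232 |

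Between 4 and 10 mm the extent needed changes more than seven-fold (for example 1,096 / 142 = 7.7). The plan's range is two-fold.

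**Results at other voxel p values**
- p 0.01, 6 mm: even 400 microlitres gives 0.53-0.98.
- p 0.001: the extent needed is 236-320 microlitres at 6 mm and 464-567 at 8 mm.
- p 0.0001: 200 microlitres gives at most 0.01 at 6 mm and 0.03-0.06 at 8 mm; 400 microlitres gives at most 0.004 at 8 mm and 0.02-0.03 at 10 mm.
- p 0.00002: 200 microlitres holds through 10 mm (at most 0.03).

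**Sections 11.3 and 11.4 side by side.** Section 11.3 also claims about a ten-fold gain in the voxel threshold from clustering. At 6 mm on the native grid, the voxel p needed without clustering is about 1.7e-6. Ten times that is about 2e-5, which is 0.002 / 0.00002 = 100 times stricter than the p used for power in Section 11.4.

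**The case against.** The strongest reply is that p < 0.002 is not an analysis rule. It comes from the power section, where it describes an outside simulation. The claimed ten-fold gain stands in Section 11.3 itself and, read literally, points to a voxel p near 2e-5, where 200-400 microlitres is safe at ordinary smoothness. Even at 0.002 the range fits data of 5-6 mm FWHM. The plan also hedges: the range is approximate, applies generally, and sits beside simulation tailored to the condition.

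Much of this stands, and it rules out three stronger readings:
- A reader might infer that the range holds 5% only for very lightly smoothed data. The documents do not support that, because the voxel p is open, and at 0.0001 or stricter the range is about adequate at 8 mm.
- A reader might infer that the simulation ignored smoothness. The same sentence names Gaussian filtering, so what the text shows is a contradiction, not proof of a wrong simulation.
- A reader might infer that the whole of primary outcome 1 is exposed. Section 11.3 tests a priori regions separately, without a cluster rule.

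The reply does not rescue the alpha statement. If each condition is simulated, its result should govern and no general volume is needed; and no source for the smoothness is named. If the voxel p is really far stricter than 0.002, alpha may hold, but then the 21-participant figure in Section 11.4 does not describe the test to be run.

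**Conclusion.** The concern holds in conditional form. Section 11.3 does not give enough to verify that whole-brain alpha is 0.05, and it contradicts itself on voxel correlation; neither point depends on the simulations. At the only voxel p that the documents link to cluster correction, 200 microlitres is sufficient only up to about 5 mm FWHM (borderline at 5 mm itself, depending on grid and sidedness) and 400 microlitres only up to about 6 mm. At 8 mm the family-wise error is 0.92-0.99 and 0.25-0.58.

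These error rates rest on the assumed slice thickness, mask, connectivity and stationary Gaussian noise; sensitivity to slice thickness and connectivity was not established. The smoothness of the actual data is unknown, so the error rate this study would have is unknown too. The point concerns whole-brain maps in both imaging arms.

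**What to change.** In Section 11.3:
- Remove the fixed volume range and the statement that voxels are taken as uncorrelated.
- Prespecify one voxel-wise p and its sidedness (for example two-sided p < 0.001), with the mask and the connectivity rule.
- Take the cluster extent for each analysis from a sign-flip permutation test, or from a simulation that uses the spatial autocorrelation estimated from that analysis's residuals.

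In Section 11.4, and in its repetition in Section 24.12, align the p < 0.002 with the threshold chosen.

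The cost is revised wording and computing time; no new data are needed. The downside is that some small clusters will no longer be reported.

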11.4. Power analysis

General fMRI power. Since fMRI is the main outcome measurement utilized in the present protocol, the key power analysis pertains to the fMRI data. However, prospective power analyses for fMRI data are complicated for several reasons. First, fMRI data are analyzed in a hierarchal manner such that both the intraparticipant variance from the time-course data and the inter-participant variance across individuals could affect statistical power. A large number of time points tend to mitigate effects of intra-participant variance, but temporal autocorrelation and scanner limitations limit the number of independent measurements per unit time and thus the number of independent time points that are collected. In addition, effect sizes and both types of variance will vary spatially. Because of this, a given study may have sufficient power to detect differences in some brain regions, but lack sufficient power in other regions where the null hypothesis is false. Finally, fMRI analysis consists of a very large number of non-independent multiple comparisons, greater than 1.5 million at the group level, necessitating correction methods less severe than a Bonferroni correction, as discussed above. Thus, a proper power analysis on fMRI data requires simulating all of these effects. Desmond and Glover (2002) have performed such a simulation. They show for a relatively modest signal change of 0.5% during a cognitive task and with an intra-participant standard deviation of 0.75% and an inter-participant standard deviation of 0.5%, that 11 participants are required for a power of 0.8 using p < 0.05. Using a false positive rate of p < 0.002, a level more consistent with a cluster size threshold to correct for multiple comparisons (Forman et al., 1995), and with the variances kept the same, approximately 21 participants are needed for an expected signal change of 0.5% and

Principal Investigator: [name].

11 participants for a signal change of 0.75%. For more than \sim 100 independent time points, power (and hence the intra-participant variance) is relatively independent of the number of time points (Desmond and Glover, 2002). All current analyses should fall within this range.

Date: March 2, 2022

Relapse vs non-relapse group comparisons. Based on previous studies comparing individuals who relapse following smoking cessation treatment to those who remain abstinent (Janes et al., 2010; Versace et al., 2011), we anticipate a medium-large effect size (Cohen's d = 0.65) when comparing relapsers vs non-relapsers across each of our neurobiological outcome measures. As we have proposed clear directional hypotheses regarding the relationship between treatment outcomes and neurobiological changes resulting from acute nicotine withdrawal, a one-tailed *t*-test model was used to calculate power. A power level $(1-\beta)$ of 0.8 was selected to achieve an appropriate balance between the ability to detect significant differences and the number of participants needed. Approximately 30 participants per group will be required to detect significant differences between these two independent groups at a nominal α level of 0.05 in a one-tailed test assuming a medium-large effect size (calculated by G*Power, http://www.psycho.uni-duesseldorf.de/abteilungen/aap/gpower3/).

Nicotine-deprived vs non-deprived condition comparisons. Estimating a dose-matched nicotine vs placebo effect size in 36 hr deprived smokers is complicated by several factors. Firstly, previous within-subject nicotine vs placebo studies have employed significantly shorter abstinence periods (e.g., 3 - 4 Hahn, Hong, Cole, or 8 hrs, Cole and Beaver). Secondly, studies addressing acute nicotine withdrawal effects using longer abstinence periods (e.g., 24 hrs) typically compare smoking deprivation to a smoke adlib condition (Azizian et al., 2010b; Field, Santarcangelo, Sumnall, Goudie, & Cole, 2006b; Kozink, Kollins, & McClernon, 2010b; McClernon et al., 2008b; McClernon, Kozink, Lutz, & Rose, 2009a; Mitchell, 2004b). Following 8 hrs of smoking deprivation, nicotine (relative to placebo) produces small to medium effects on self-report withdrawal symptoms, mood and craving measures (Cohen's d = 0.15 to 0.52), medium effects on behavioral measures (d = 0.48 to 0.618) (Beaver et al., 2011; Cole et al., 2010). Effects of 12 to 24hrs of smoking deprivation (relative to adlib smoking) on self-reported craving and affect/mood vary from medium to large (d = 0.51 to 4.91). The same deprivation periods produce small to medium effect sizes (d = 0.23 to 1.435) for go-nogo, attention and delay discounting tasks with larger effects on RT and discounting rate and smaller effects on error rates.

In the current study we aim to increase the severity of nicotine-withdrawal effects by employing a 36 hour deprivation period. At the same time, individual differences in responsivity to nicotine replacement will likely reduce between-condition effects relative to smoking deprivation vs smoke adlib studies cited above. Together the above studies suggest that the weakest effects of a dose-matched nicotine vs placebo manipulation in 36 hr deprived smokers smoking deprivation manipulation will arise for behavioral measures and will be medium in size (d = 0.5). We selected a power level (1- β) of 0.80 to achieve an appropriate balance between the ability to detect significant differences and the number of participants needed. Assuming an alpha-level of 0.05, a correlation among repeated measures of r = 0.5 and a medium effect size, approximately 35 participants will be required to achieve a power of 0.80 (calculated by G*Power http://www.psycho.uniduesseldorf.de/abteilungen/aap/gpower3/).

Motivation to quit by nicotine-deprivation. To generate an estimated effect size for a 2 (treatment seeking vs non-treatment eeking) x 2 (deprived vs non-deprived) we referred to the single study conducted to date comparing treatment seeking smokers to non-treatment seeking smokers (Wilson et al., 2012). In this study, which employed self-report physiological and neuroimaging outcome measures, the smallest effect size reported for a 2 x 2 between-within interaction, where the between subjects factor was treatment seeking status, was $\eta^2 = .08$. Based on an effect size of $\eta^2 = .08$, and a power of 0.80, and an estimated correlation between repeated measures of 0.5, the required sample size to detect a true 2 x 2 between-within interaction effect is 26 individuals.

Genotype by nicotine-deprivation. To derive an estimated effect size for the genotype by nicotine-deprivation interaction we examined effects of the 5-HTTLPR polymorphism on pharmacological manipulations where conditions are varied within-subjects. Genotype by treatment effects on behavioral and self-report outcome

Principal Investigator: [name].

measures in these studies display a small to large effect size (d = 0.30 to 0.90) (Kellner et al., 2009; Marsh et al., 2006; Thakur, Grizenko, Sengupta, Schmitz, & Joober, 2010). Recently, (Minnix et al., 2011) reported a large effect (d = 1.45) of the 5-HTTLPR polymorphism on startle reactivity in overnight deprived smokers following nicotine vs placebo nasal spray. Although the effect of the serotonin transporter polymorphism on brain (BOLD or EEG/ERP) activity changes following nicotine or smoking deprivation has yet to be investigated, large effect sizes (d > 0.80) have been reported for a smoking deprivation by COMT genotype interaction (Wang et al., 2008).

Date: March 2, 2022

Due to the large variance in reported effects we conducted two power analyses assuming a medium (d = 0.50) and large effect size (d = 0.80) effect size. Based on these analyses and assuming a correlation among repeated measures of r = 0.5, we would require approximately 16 to 35 individuals to achieve an 80% chance of detecting a genotype by nicotine-deprivation effect in the current study across our BOLD and behavioral indices (calculated by G*Power, http://www.psycho.uniduesseldorf.de/abteilungen/aap/gpower3/).

Correlational. Bivariate partial correlations (controlling for nicotine dose) will be conducted between the change in BOLD, ERP/EEG, psychophysiological and neuroendocrine markers, behavioral and self-report under nicotine-deprivation (relative to nicotine satiety). Large effects (d > 0.80) are typically observed between changes in self-report (e.g., craving, withdrawal symptoms) and BOLD measures (e.g., insula or amygdala activity or functional connectivity) during smoking abstinence relative to smoke adlib (Cole et al., 2010; Kozink et al., 2010a; McClernon et al., 2009b). Similarly large effect sizes are reported between changes in behavioral indices (e.g., RT variability) and BOLD responses (e.g., PCC task response) under nicotine (relative to placebo) in minimally deprived smokers (Hahn et al., 2007). Large effect sizes also arise between BOLD responses and neuroendocrine and psychophysiological markers (Ahs, Sollers, Furmark, Fredrikson, & Thayer, 2009; Drevets et al., 2002) as well as between behavioral indices and time-to-smoke in the laboratory relapse model (Dallery & Raiff, 2007). Based on a slope of 0.59 between each predictor and outcome measure (a large effect size according to J. Cohen, 1988) a sample size of at least 20 would be required to achieve a power of 0.80. (Calculated by G*Power, http://www.psycho.uniduesseldorf.de/abteilungen/aap/gpower3/).

Mediation Analyses. Based on the literature reviewed above, we expect a large effect size between each predictor, outcome and mediation variable in the mediation models described above. Based on a large effect size for paths *a* and *b*, Fritz and McKinnon (2007) suggest a sample of 35 to achieve a 0.80 power to detect each mediation effect with Prodclin.

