10.1. Primary outcomes measures

1) Change in BOLD signal and FC related to task parameters, between drug conditions: will provide important insight into the neurobiological mechanisms underlying acute nicotine withdrawal, in particular those related to anhedonia, negative affect, inhibitory control and impulsive decision making.

Date: March 2, 2022

- 2) Behavioral performance on each of the tasks assessing inhibitory control processes, reward responsiveness, amygdala, striatal, BNST reactivity and impulsive decision making (e.g., reaction time, error rate, hit rate, reward bias): will provide task-related parameters necessary for analysis of BOLD data. Performance data will function as a secondary outcome by providing behavioral validation of acute nicotine withdrawal effects.
- 3) Self-reported craving, withdrawal symptoms and mood/affect: will be employed as regressors in the analysis of task and resting BOLD data. They will also provide the primary means of validating the acute nicotine withdrawal manipulation.
- 4) Smoking status at 1, 6 and 12 months: Smoking status (relapse vs abstinent) at each of the follow-up time points will be based on 7-day point prevalence defined as no smoking (not even a puff) or use of any tobacco products for the past 7 days. This is a standard method of assessing abstinence and dichotomizing relapse status at follow-up (Keating & Siddiqui, 2006; Leventhal et al., 2008; Swan et al., 2010b). Whenever abstinence at follow-up is assessed in-person, self-reported abstinence will be corroborated with breath CO and urine cotinine levels.

10.2. Secondary outcome measures include:

- 4) MRS for glutamate concentration: Glutamate concentration at the PFC and hippocampus is expected to change as a function of acute nicotine withdrawal and may also play a role in the expected reduction in VS reactivity and anhedonia.
- 5) Plasma ACTH and cortisol: are expected to increase as a function of acute nicotine withdrawal and is expected to play role in both anhedonia and negative affective symptoms, potentially by acting at the amygdala, BNST and VS.
- 6) Resting state CBF from ASL: To test for changes in neural activity (i.e., not connectivity) at rest it is necessary to employ a measure which does not require a baseline. CBF provides such a measure as changes in blood flow are referenced to a common arterial location outside of the brain.

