11.5. Accrual number request, taking into account screening/dropouts

Treatment-seeking smokers. In the current study, an individual will be considered a completer if they meet the following criteria: 1) have completed the two pre-treatment scan visits; 2) have set a quit date; 3) attempted to quit for at least 24 hours; 4) we have been able to establish their quit status (i.e., relapsed vs non-relapse) at 1, 6 and 12 months following their last treatment visit. Based on the power analyses above we anticipate that a minimum group size of 30 in each of our two relapse groups (relapse vs abstinent) at each follow-up time point (1, 6 and 12 months) would provide a reasonable level of statistical power allowing for the detection of effects of interest in the present study. Based clinical trials of varenicline with similar follow-up time points (Aubin et al., 2008; Keating & Siddiqui, 2006; Krebs & Sherman, 2012; Swan et al., 2010a; Tsai et al., 2007), we estimate that 35% of completers at 12 months will meet criteria for 7-day point prevalent abstinence. The 12 month follow-up is the point at which we would expect our abstinent group to be smallest. Achieving a minimum of 30 abstinent smokers at 12 months would require 85 completers (i.e., 35% abstinence rate). Based on an expected 30% attrition rate at 12 months (Keating & Siddiqui, 2006) a total of 120 treatment-seeking smokers (85 completers) is therefore requested.

Non-treatment seeking smokers. An individual will be considered a completer if they complete procedures outlined for Phase 1 of the protocol (see Section 4 Study Design and Methods). Based on power analyses described above and in Section 10.4 we anticipate that 35 non-treatment seeking smokers with complete

Principal Investigator: [name].

Date: March 2, 2022

and useable data would provide a reasonable level of statistical power allowing for the detection of effects of interest in the present study. However, since acute nicotine-withdrawal effects may increase head movement and given the potential for unforeseeable errors during data collection, an estimated 20% of the participants who complete all phases of the study will likely be removed from the final analyses. Thus, a total of 42 non-treatment seeking smokers is requested.

12. Human Subjects Protection

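### Section 11.4 calls d = 0.5 the weakest deprivation effect, but the effects it cites go down to 0.15 and 0.23; the 35 it derives gives 0.80 power only from d of about 0.49

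*Combined protocol and SAP*

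**What the plan says.** The Main Study compares a nicotine patch with a placebo patch. Both conditions include 36 h without smoking (Section 2, Design).

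For this contrast, Section 11.4 reviews two sets of earlier studies.

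- **Nicotine versus placebo, 8 h of abstinence.** The plan reports that "nicotine (relative to placebo) produces small to medium effects on self-report withdrawal symptoms, mood and craving measures (Cohen's d = 0.15 to 0.52"). For behavioral measures it gives d = 0.48 to 0.618.
- **Deprivation of 12 to 24 h versus ad lib smoking.** Self-reported craving and mood are given as d = 0.51 to 4.91. For tasks: "The same deprivation periods produce small to medium effect sizes (d = 0.23 to 1.435) for go-nogo, attention and delay discounting tasks". Error rates are said to lie at the smaller end.

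The section then makes two adjustments without putting numbers on them. The 36 h period is meant to make withdrawal more severe. Varying response to nicotine replacement is expected to shrink effects compared with the ad lib studies. It concludes that the weakest effects of the "manipulation will arise for behavioral measures and will be medium in size (d = 0.5"). The sample size follows: "Assuming an alpha-level of 0.05, a correlation among repeated measures of r = 0.5 and a medium effect size, approximately 35 participants" for power 0.80.

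Section 11.5 uses the number for one group: "we anticipate that 35 non-treatment seeking smokers with complete" and usable data would give reasonable power.

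Section 10.1 lists self-reported craving, withdrawal and mood as primary outcome 3 and says of these measures: "They will also provide the primary means of validating the acute nicotine withdrawal manipulation".

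**The concern.** A sample size set for the weakest expected effect should cover all the others. A reader of Section 11.4 will therefore take 35 as enough for every measure in the deprivation comparison.

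The cited figures do not allow that. In the set with the same type of comparator as this trial, self-report is weaker than behavior and goes down to 0.15, which reverses the plan's ranking. In the ad lib set behavior is indeed weaker, but its floor is 0.23, and the plan expects its own contrast to give less than those studies did. A floor that is both behavioral and about 0.5 appears only when self-report is read from the ad lib set and behavior from the 8 h set.

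At stake is the stated power for self-report, which is a primary outcome and the main check that the manipulation worked, and for error rates.

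**Working it through.** **Inputs.** From Section 11.4: alpha 0.05, r = 0.5, d = 0.5, power 0.80, N about 35. Planned completers are 85 + 35 = 120 (Précis). Section 11.4 says only "Assuming an alpha-level of 0.05" and does not give sidedness. Two-sided is assumed because it reproduces the stated N.

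**Formula.** For a paired t-test, the standardized mean difference is dz = d / sqrt(2(1 − r)). With r = 0.5 the divisor is sqrt(1) = 1, so dz = d. Power comes from the noncentral t distribution with n − 1 degrees of freedom and noncentrality dz × sqrt(n).

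**Reproducing the plan.** At d = 0.5, n = 34 gives power 0.808. At n = 35 the noncentrality is 0.5 × 5.916 = 2.96 and power is 0.820. A repeated-measures ANOVA with f = 0.25 and two measures also gives 34. A one-sided test would need only 27. The stated figure of about 35 is reproduced.

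**Same calculation at the other cited effects.**

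| d | Source in 11.4 | N for 0.80 | Power, n = 35 | Power, n = 85 | Power, n = 120 |
|---|---|---|---|---|---|
| 0.15 | self-report floor, nicotine vs placebo, 8 h | 351 | 0.14 | 0.28 | 0.37 |
| 0.23 | task floor, deprivation vs ad lib, 12–24 h | 151 | 0.26 | 0.55 | 0.71 |
| 0.48 | behavioral floor, nicotine vs placebo, 8 h | 37 | 0.79 | 0.99 | >0.99 |
| 0.50 | planning value | 34 | 0.82 | >0.99 | >0.99 |
| 0.52 | self-report ceiling, nicotine vs placebo, 8 h | 32 | 0.85 | >0.99 | >0.99 |

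**Smallest d with 0.80 power.** This is 0.487 at n = 35, 0.307 at n = 85 and 0.258 at n = 120.

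**Which n applies.** Section 11.2 puts both groups in one repeated-measures model, with treatment-seeking status as a between-subjects factor. The planned test of the deprivation effect therefore uses about 120 completers. The figure of 35 applies when the non-treatment seekers are analyzed alone.

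**Sensitivity at d = 0.15.** Power with 35 is 0.11 if r = 0.3, 0.20 if r = 0.7 and 0.49 if r = 0.9. With 120 it is 0.28, 0.56 and 0.95. These values of r are assumptions; the plan gives only 0.5. A one-sided test at r = 0.5 gives 0.22 with 35 and 0.50 with 120.

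**The case against.** The strongest reply is that 35 is a stated requirement, not the sample for this test. The pooled model has 120 completers and detects d of about 0.26. The number may be larger still, because treatment-seeking completers are defined by follow-up quit status (Section 11.5) while this contrast needs only the two pre-treatment scans. If all 120 + 42 = 162 enrollees supplied both scans, power would be 0.83 at d = 0.23 and 0.48 at 0.15. This stands, and it limits the consequence. It does not make the weakest-effect sentence correct.

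Second, no cited study matches both the comparator and the 36 h duration, and the plan says openly that it is weighing two literatures. The longer-abstinence set does support behavior as the weaker domain. That also stands, but the same set puts the behavioral floor at 0.23, and the gain expected from 36 h is never quantified.

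A reader might infer more than the documents support:

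- **That the arithmetic is wrong.** It is not. The issue is the choice of planning effect.
- **That self-report in this trial will show d = 0.15.** That value comes from 8 h of abstinence. It is the bottom of a range that runs to 0.52, where 35 participants do give 0.85.
- **That the correlation and mediation analyses run separately by group are undersized for this reason.** Section 11.4 sizes them separately, at 20 and 35 on large effects, and Section 11.5 refers to the power analyses in general.
- **That a null result in the 35 would be read as a failed manipulation.** No section says so.

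**Conclusion.** The point holds as a misstatement of the planning effect. Calling d = 0.5 the weakest effect is inconsistent with both sets of studies that Section 11.4 cites, and 35 participants reach the stated 0.80 only for d of about 0.49 or more. In the pooled test of Section 11.2 the shortfall is limited to d below about 0.26, where power is 0.71 at 0.23 and 0.37 at 0.15. It applies in full (0.26 and 0.14) only if the non-treatment seekers are tested alone.

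This rests on a two-sided 0.05 test, r = 0.5, cited effects on the same scale as the planning d, no multiplicity adjustment and no loss of data. The pooled figures treat the 120 as one sample of paired differences, without the group factor and dose covariate. A higher correlation, or a larger effect at 36 h, would narrow the gap. The plan gives no figure for either beyond r = 0.5.

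**What to change.** In Section 11.4, remove the statement that the weakest effect is behavioral at d = 0.5, or justify d = 0.5 for self-report and error rates at 36 h. State the effects detectable with 0.80 power at the planned sizes: d = 0.49 at 35, 0.31 at 85 and 0.26 at 120. State also that the pooled deprivation effect in Section 11.2 is the test of the self-report outcome used to validate the manipulation.

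In Section 11.5, state that 35 non-treatment seekers give 0.80 power for this comparison only at d of about 0.49 or more.

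These are changes of wording. No participants or procedures are added; the cost is a less favorable stated figure.
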